## Study Protocol

### Background

Decreasing inappropriate utilization of the Emergency Department (ED) is a priority for the Geisinger health system. ED visits may be avoided if patients first call the system to get appropriate guidance for their concerns or are otherwise better informed about reasons to visit the ED vs. other, potentially more appropriate resources such as urgent care and primary care facilities. The study team is working to reduce ED utilization by including additional information in adult outpatient After Visit Summaries (AVSs).

### Objectives

The study will involve A/B testing different AVS versions, including a version that encourages patients to contact Geisinger via different contact methods, a version that includes a map to the patient's closest urgent care location and accompanying information about urgent care, and a version that includes a self-triage guide. A standard-practice control group will receive the current standard AVS. Analysis results will be assessed to determine which version is most effective at reducing ED use.

### Design

This study is a randomized controlled trial with 4 study arms. Patients will be randomized to receive or not receive a modified AVS after outpatient in-person or telehealth visits.

### Methods

At the time of a patient's first qualifying appointment during the study period, patients will be randomized into the following study arms:

1. **Standard practice:** Patients in this arm will receive the current standard practice AVS.
2. **Contact us first:** Patients in this arm will receive the standard AVS, plus information on how to contact Geisinger if they need medical attention.
3. **Contact us first + urgent care map:** Patients in this arm will receive the standard AVS, plus information on how to contact Geisinger if they need medical attention, plus a map of their nearest Geisinger urgent care location and additional information about urgent care.
4. **Contact us first + urgent care map + self-triage:** Patients in this arm will receive the standard AVS, plus information on how to contact Geisinger if they need medical attention, plus a map of their nearest Geisinger urgent care location and additional information about urgent care. This arm will also receive a self-triage chart, with common reasons patients go to the ED and situations where seeking alternative care might be appropriate.

### Sequential Design

We will use a group sequential design with O'Brien-Flemming alpha spending and beta spending (Lakens et al., 2021), with optional stopping for futility. We will perform one interim look after collecting data from 109,346 patients (50% of the sample) and the final look after

completing data collection with 218,692 patients. We will stop after the interim look if  $p < .005575$  (i.e., a much larger effect than expected) for the contrast between *any* of the 3 experimental arms and control in *Analysis 1* below. We may also stop for futility if  $z > -0.192$  (i.e., an effect in the opposite direction to our expectations) for *all* 3 contrasts between experimental arms and control in *Analysis 1* below. All tests will be 1-sided tests with an overall alpha of .05.

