## Power Analysis

With a traditional RCT design and 215,000 patients, we would have 95% power to detect a reduction in avoidable ED use in the 30 days following the appointment from 3.88% to 3.50% (9.80% relative reduction) with one-tailed alpha of .05. The target effect size and number of patients are largely informed by practical considerations regarding the acceptable duration of the intervention (approximately 6 months), with an effect deemed useful if achieved.

We next determined that the inflation factor based on the sequential design described above was 1.01717. We multiplied the inflation factor by the fixed design sample size (215,000 \* 1.01717) for a sample size of 218,692.

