## Project Status

All patients have been enrolled, but we have not extracted the final outcome data.

We ran an interim analysis on preliminary outcome data, as described above. Although effect sizes met our optional stopping for futility criteria ( $zs < -0.192$ ), we decided to keep running the study to be able to run all final analyses at full power.

We were unable to turn off the intervention immediately once reaching our target sample size, so we exceeded our preregistered sample size. Our final analyses will be based on the full list of patients enrolled until the intervention stopped. We will also run the primary outcome analyses on the subset of patients enrolled through the day we reached the preregistered sample size.

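### Does the loose description of the interim efficacy bound, or a 95% power figure that covers only one contrast, call for a change to the plan?

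*Combined protocol and SAP*

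**What the plan says.** The Sequential Design section sets one interim look at 109,346 patients and a final look at 218,692, with O'Brien-Fleming-type alpha and beta spending. The efficacy rule is p < .005575, described as follows: "i.e., a much larger effect than expected) for the contrast between *any* of the 3 experimental arms and control". Futility is an optional stop with a z value of magnitude 0.192, required of all three contrasts. The section ends: "All tests will be 1-sided tests with an overall alpha of .05".

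The Power Analysis section begins from a conventional fixed design with 215,000 patients, which gives "95% power to detect a reduction in avoidable ED use in the 30 days following the appointment from 3.88% to 3.50"%. On where that effect came from, it says: "The target effect size and number of patients are largely informed by practical considerations regarding the acceptable duration of the intervention". It then links the sample size to the stopping rules: "We next determined that the inflation factor based on the sequential design described above was 1.01717". Multiplying gives 218,692.

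The Project Status section reports the position now: "All patients have been enrolled, but we have not extracted the final outcome data". The interim analysis had been run by then, and the study had continued so that the final analyses would have full power.

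**The concern.** Two statements looked wrong.

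First, a reader of the gloss would take an early efficacy stop to be a remote event. The only effect size in the plan is the 3.88% to 3.50% target. If the bound lies close to that target, a stop at half the data was near even odds for any one arm that worked as hoped.

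Second, the inflation factor is said to rest on the sequential design just described, so a reader could take 95% as the power for each arm under that design. But the rule ends the whole trial when any of three contrasts crosses, and the plan does not say how the other arms would then be judged. Analysis 1 tests each version separately, and the Objectives ask which version works best. The interventions are cumulative, so more than one effective arm is a natural scenario. A stop triggered by one arm could have left another effective arm with half its data and no declared result.

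**Working it through.** **Inputs.** From Sequential Design: one-sided alpha .05, looks at 109,346 and 218,692, efficacy p < .005575, futility magnitude 0.192. From Power Analysis: 3.88% versus 3.50%, 95% power, 215,000 patients, inflation 1.01717. Assumption: four equal arms, since no allocation ratio is stated.

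**Step 1. Reproduce the fixed-design power.** Per arm, 215,000/4 = 53,750.
- SE = sqrt((.0388 × .9612 + .0350 × .9650)/53,750) = 0.1150 percentage points.
- Power = Φ(0.38/0.1150 − 1.645) = Φ(1.66) = 95.2%.

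This matches the stated 95%. The figure is therefore for one arm against control, with four equal arms and unadjusted alpha.

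**Step 2. Reproduce the sequential figures.** For one contrast with a look at 50% and non-binding futility:
- Alpha spent at the interim = 2 × (1 − Φ(1.96/√0.5)) = .005575, so z = 2.538.
- The final bound is z = 1.6621.
- The drift for 95% power is 3.3178. The fixed-design value is 2 × 1.6449 = 3.2897.
- Inflation = (3.3178/3.2897)² = 1.01717.
- Expected interim z at the target = 3.3178/√2 = 2.346.
- The same .005575 of beta is spent at the interim, so the futility value is 2.346 − 2.538 = −0.192 (positive z = reduction).

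The nominal p, the inflation factor and the magnitude of the futility value all agree with the plan. The direction of the futility inequality is a separate matter and does not enter here.

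**Step 3. Place the bound against the target.**
- From the design alone: 2.538/2.346 = 1.08. A contrast at the target crosses with probability Φ(−0.192) = 42%.
- From the event rates with 109,346/4 = 27,336.5 per arm: SE = 0.1612 points. The bound is 2.538 × 0.1612 = 0.409 points, a 10.5% relative reduction (0.409/3.88). Then 0.409/0.38 = 1.08, crossed 43% of the time.

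**Step 4. Power under the stop-on-any rule.** This is a normal-approximation simulation with a shared control, equal arms and effective arms at the target. The plan does not say what happens to uncrossed arms after a stop, so both cases are shown.

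| Effective arms | Interim efficacy stop | Per arm, uncrossed not declared | Per arm, uncrossed tested at z = 1.645 on interim data | At least one effective arm (uncrossed not declared) |
|---|---|---|---|---|
| 1 | 43% | 95% | 95% | 95% |
| 2 | 59% | 80% | 92% | 98.8% |
| 3 | 67 to 68% | 71 to 72% | 90% | 99.5% |

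The small ranges come from using an unpooled or a pooled variance in the test.

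**Step 5. What the trial as run can do.** With 218,692/4 = 54,673 per arm, SE = 0.1140 points. Power at the final bound = Φ(0.38/0.1140 − 1.6621) = Φ(1.67) = 95.3% per contrast.

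**The case for a change.** The best case for acting is that the gloss misdescribes the rule and would take only a few sentences to correct. The final outcome data were not yet extracted, so a correction could not look driven by results. An 8% excess over the target is not a much larger effect, and the inflation factor plainly comes from a one-contrast calculation. All of this stands as arithmetic.

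It does not stand as a reason to amend. The plan never calls 3.88% to 3.50% its expected effect. It presents it as feasible within the intervention period and useful if achieved. If the investigators privately expected half of it (an assumption for illustration), the bound would be about 2.15 times their expectation (0.409/0.19) and crossed about 9% of the time, so the gloss would be fair. The fault is then an undefined word in an aside to an exact threshold.

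The 95% is attached to the fixed design, where it is correct. The plan claims no per-arm power under stop-on-any. The 80% and 71 to 72% figures depend on a rule for uncrossed arms that the documents do not contain; under the other rule shown, the loss is 3 to 5 points. With one effective arm there is essentially none. Power to find at least one effective arm is 95% or more throughout.

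**Conclusion.** No change is needed. The gloss is loose: against the plan's only effect size the bound is 1.08 times the target and is crossed 42 to 43% of the time. The plan could also have said that its 95% is per contrast. But the operative threshold, the inflation factor and the fixed-design power all reproduce. The possible per-arm loss applied only if the interim had ended the trial, and it did not. The final contrasts use the full sample, with about 95.3% power each at the target and at 218,692 patients. New wording would describe a rule that did not end the trial, and no estimate, test or conclusion would move.

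This rests on equal allocation, which the plan does not state but which reproduces its 95%; on reading the target as the reference effect; and on the Project Status report that enrolment ran to completion. The 95.3% is for each contrast taken alone and makes no allowance for testing three.

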## Power Analysis

With a traditional RCT design and 215,000 patients, we would have 95% power to detect a reduction in avoidable ED use in the 30 days following the appointment from 3.88% to 3.50% (9.80% relative reduction) with one-tailed alpha of .05. The target effect size and number of patients are largely informed by practical considerations regarding the acceptable duration of the intervention (approximately 6 months), with an effect deemed useful if achieved.

We next determined that the inflation factor based on the sequential design described above was 1.01717. We multiplied the inflation factor by the fixed design sample size (215,000 \* 1.01717) for a sample size of 218,692.

## Project Status

All patients have been enrolled, but we have not extracted the final outcome data.

We ran an interim analysis on preliminary outcome data, as described above. Although effect sizes met our optional stopping for futility criteria ( $zs < -0.192$ ), we decided to keep running the study to be able to run all final analyses at full power.

We were unable to turn off the intervention immediately once reaching our target sample size, so we exceeded our preregistered sample size. Our final analyses will be based on the full list of patients enrolled until the intervention stopped. We will also run the primary outcome analyses on the subset of patients enrolled through the day we reached the preregistered sample size.

## Process for Determining a Patient's Nearest Urgent Care

A patient's nearest urgent care will be determined by their zip code in Geisinger's Electronic Health Record. Zip code locations will be defined as population-weighted centroids (obtained from <https://hudgis-hud.opendata.arcgis.com/datasets/HUD::zip-code-population-weighted-centroids/>) where available. For some zip codes (P.O. Box zip codes in particular), population-weighted centroids are not available. In those cases, we will use the zip code's approximate centroid obtained from the USPS Zip Code Database (<https://www.unitedstateszipcodes.org/zip-code-database/>).

Distance to the nearest Geisinger urgent care location for each zip code will be calculated using the following process:

1. For each zip code in PA, NY, and NJ (states that are within or sufficiently close to the Geisinger service area), we will compute the Haversine distance to each urgent care location
2. For each zip code, we will determine if at least one urgent care location is within 40 miles of the zip code centroid

3. If more than one location is within 40 miles and under a 10 mile difference in distance between zip code centroid and each of those two clinic locations (e.g., if one clinic is 10 miles away and another is 15 miles away, a 5 mile difference), we will use the Google Maps API to determine which clinic is the closest driving distance in minutes

For patients assigned to one of the arms that includes an urgent care map, we will show a map to the closest clinic if the Haversine distance is under 40 miles from the centroid of the patient's zip code. For patients with zip codes farther than 40 miles from a Geisinger urgent care location, we will show a map that includes all urgent care locations with information on how to find their nearest urgent care.

## Statistical Analysis Plan

### Planned Analyses

**Primary Outcome:** Inappropriate ED visits (y/n) [Time Frame: In the 30 days following the appointment]

We will apply the NYU algorithm (Ballard et al., 2010) to determine whether an ED visit is inappropriate.

We will use one of the following two methods:

1. Epic tool: Geisinger is working to implement a tool in Epic that can automatically run the NYU algorithm and identify inappropriate (or "non-emergent") ED visits. If this tool is running prior to data analysis, we will use it to identify inappropriate ED visits for our primary outcome.
2. Custom code: If the Epic tool is not yet implemented prior to our data analysis, we will pull, for each ED visit, the primary ICD code for the visit and use custom code to determine whether the visit was inappropriate, following the methods described in Ballard et al. (2010) or the most up-to-date version of the algorithm we have access to at the time of data analysis.

**Question 1:** Do AVSs decrease inappropriate ED visits when including information about how to contact Geisinger if patients need care?

**Analysis 1 (Confirmatory):** We will test the hypothesis that each of the individual modified AVS versions decreases the likelihood patients will visit the ED in the 30 days following their visit. We will run an OLS regression including a categorical predictor variable coding for experimental arm (0 = standard practice arm, 1 = contact us first arm, 2 = contact us first + urgent care arm, 3 = contact us first + urgent care map + self-triage arm).

**Question 2:** Do AVSs decrease ED visits when including an urgent care map, beyond modified AVS version without an urgent care map?

**Analysis 2 (Exploratory):** We will run an OLS regression including only experimental arms with modified AVSs. We will include a predictor variable indicating whether each patient's AVS version includes a map (0 = no map, contact us first arm; 1 = map, contact us first + urgent care map arm and contact us first + urgent care map + self-triage arm).

**Question 3:** Do AVSs decrease ED visits when including a self-triage tool, beyond modified AVS versions without a self-triage tool?

**Analysis 3 (Exploratory):** We will run an OLS regression including only experimental arms with modified AVSs. We will include a predictor variable indicating whether each patient's AVS version includes a self-triage chart (0 = no self-triage chart – contact us first arm and contact us first + urgent care map arm; 1 = self-triage chart – contact us first + urgent care map + self-triage arm).

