## **Covariates**

Because the ultimate call to action (seeking care outside the ED) is likely to depend on proximity to the ED and alternate care options, all the regressions described above will include as covariates the driving distance in miles to the closest Geisinger ED and the driving distance in miles to the closest Geisinger urgent care location. Specifically, covariates will reflect the distance from the closest Geisinger ED and closest Geisinger urgent care location of the patient's zip code in the Geisinger electronic health records. Distances between each enrolled patient's zip code centroid and ED/urgent care locations will be computed using the same process described above in the section **Process for Determining a Patient's Nearest Urgent Care**, with the added step of computing the driving distance in miles for each zip code.

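### Exploratory Analyses 2 and 3 compare pooled, nested AVS versions, so the map and self-triage coefficients do not isolate what each added feature contributes, and no adjacent-arm test is specified

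*Combined protocol and SAP*

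**What the plan says.** Arms are numbered here as in Methods: 1 standard practice, 2 contact us first, 3 contact plus urgent care map, 4 contact plus map plus self-triage. (Analysis 1 codes the same arms 0 to 3.)

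Methods makes the modified arms cumulative. Arm 3 is arm 2 "plus a map of their nearest Geisinger urgent care location and additional information about urgent care". Arm 4 repeats all of that and adds the chart: "This arm will also receive a self-triage chart, with common reasons patients go to the ED". No arm has the chart without the map.

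Under Planned Analyses, Question 2 asks: "Do AVSs decrease ED visits when including an urgent care map, beyond modified AVS version without an urgent care map". Analysis 2 answers it in the three modified arms with one indicator, 0 for arm 2 and "1 = map, contact us first + urgent care map arm and contact us first + urgent care map + self-triage arm".

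Question 3 asks: "Do AVSs decrease ED visits when including a self-triage tool, beyond modified AVS versions without a self-triage tool". Analysis 3 uses the same three arms with one indicator, "0 = no self-triage chart – contact us first arm and contact us first + urgent care map arm", and 1 for arm 4.

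Neither model carries the other feature's indicator. Under Covariates, "all the regressions described above will include as covariates the driving distance in miles to the closest Geisinger ED" and the corresponding distance to urgent care; nothing else is added. Analysis Notes adds one more arm comparison, any modified AVS against standard practice. No test of arm 3 against arm 2, or of arm 4 against arm 3, is written anywhere. Other Pre-specified Outcomes applies the same models to urgent care visits, calls and portal messages.

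**The concern.** Under Objectives, "Analysis results will be assessed to determine which version is most effective at reducing ED use". Within a nested set of versions, whether each longer version improves on the one before it is answered by the adjacent-arm differences: arm 3 minus arm 2 for the map, and arm 4 minus arm 3 for the chart. Analyses 2 and 3 are the only formal comparisons specified among the modified versions, and both mix these two differences.

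A coefficient attached to an indicator for including a map will readily be reported as the effect of the map. If only the chart works, half of its effect (with equal arms) appears in the map coefficient, and the reverse holds in Analysis 3. The mixing can also hide an effect: a map that raises visits can show a coefficient of zero if the chart lowers them enough. What is at stake is the choice of which features to keep, for the primary outcome and the three others.

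**Working it through.** **Inputs.** Rates of 3.88% and 3.50%, 95% power, one-sided .05, 215,000 patients and inflation factor 1.01717 (Power Analysis); four arms (Design). The allocation ratio is not stated, so equal arms are assumed and then varied. The contact-only arm is assumed to be at 3.88%, and this is varied too. The distance covariates are left out; randomisation balances them, so they do not change what the coefficients estimate.

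**The plan's own figure.** 215,000/4 = 53,750 per arm gives 95.2% power for 3.88% against 3.50% (normal approximation, pooled variance); 53,267 per arm would give 95%. 215,000 × 1.01717 = 218,691.55, which rounds up to 218,692. The plan's figure reproduces. Equal arms are then 218,692/4 = 54,673.

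**What each coefficient estimates.** Let M = arm 3 − arm 2 and T = arm 4 − arm 3. A single binary predictor in OLS returns a difference of pooled means.

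- Analysis 2: (n3·μ3 + n4·μ4)/(n3 + n4) − μ2 = M + T·n4/(n3 + n4)
- Analysis 3: μ4 − (n2·μ2 + n3·μ3)/(n2 + n3) = T + M·n2/(n2 + n3)

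With equal arms these are M + T/2 and T + M/2. Each equals its own feature's effect only if the other feature adds nothing. Unequal allocation changes the weights but does not remove the mixing.

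**Two illustrations (equal arms).** If each feature lowers visits by 0.19 points, both coefficients are −0.19 − 0.095 = −0.285 points. If the map raises visits by 0.19 and the chart lowers them by 0.38, the map coefficient is 0.19 − 0.19 = 0.

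**How often an inert feature's coefficient is significant.** The contrast weights for arms 2, 3, 4 are (−1, ½, ½) for Analysis 2 and (−½, −½, 1) for Analysis 3. The variance is the sum of w²·p(1 − p)/54,673, and the rejection probability is Φ(|effect|/SE − 1.645).

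Worked case, Analysis 3 with an inert chart and a map effect of 0.19 points: rates 3.88%, 3.69%, 3.69%; coefficient −0.095; SE 0.0991; 0.095/0.0991 − 1.645 = −0.69; probability 24.6%.

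| Other feature's effect (points) | Analysis 2, map inert | Analysis 3, chart inert | Adjacent-arm contrast for the inert feature |
|---|---|---|---|
| 0 | 5% | 5% | 5% |
| 0.095 | 12.0% | 12.1% | 5% |
| 0.19 | 24.1% | 24.6% | 5% |
| 0.38 | 59.8% | 62.2% | 5% |

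A simulation of the unadjusted OLS tests (40,000 runs per case) agrees with the three non-zero rows to within one percentage point.

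**Sensitivity at 0.19 points.**

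- Contact-only arm already at 3.50%: 26% for both analyses.
- 98% of patients, the share expected in the primary analysis sample: 24% for both.
- 10% more patients (the excess enrolment noted in Project Status is not quantified): 26% for both.
- Same three-arm total, arm 3 double-sized: 14–15%. Arm 2 or arm 4 double-sized: 26–32%.

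At 0.38 points, the two allocation ranges become 31–33% and 64–77%.

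**Price of the adjacent contrast.** The SE ratio is √(2/1.5) = 1.155. For a map effect with an inert chart, power goes from 59.8% (pooled) to 50.0% (arm 3 vs arm 2) at 0.19 points, and from 98.5% to 95.4% at 0.38 points.

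**The case against.** The best defence is that the plan does what it says. Question 2 refers to a version (singular) without a map, and there is one; Question 3 refers to versions (plural) without a self-triage tool, and there are two. The coding lists exactly those arms, so the pooling looks deliberate. Nothing in the documents says that a coefficient isolates a component. On that reading, the 12%, 24–25% and 60–62% figures are not type I error rates of the planned tests but their power to detect a real pooled difference. This stands: the tests are valid for the contrasts they define, and credit is false only if a coefficient is read as the effect of the feature its indicator names.

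Second, Analysis 1 estimates every version against standard practice, so the versions can be ranked and M and T obtained by subtracting coefficients. That is right for point estimates. No test or interval for those differences is specified.

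Third, the 0.38-point case requires one feature to deliver alone the whole effect that the trial was powered to find for a modified AVS against standard practice. Project Status reports interim results meeting the futility criteria, although its printed inequality runs opposite to the one under Sequential Design, so little weight can rest on it. The 0.38-point row is therefore an extreme case; the smaller effects are the fairer guide.

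Fourth, pooling buys precision, and both analyses are labelled exploratory. Both points are true, and they limit the severity.

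None of this removes the point. Both questions ask what a feature adds beyond versions without it, and the plan does not say whether the pooled or the incremental quantity is meant.

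**Conclusion.** The concern holds, as a minor point. That the two coefficients mix M and T follows from the arm definitions and the coding alone. The size depends on assumptions: with equal arms, a contact-only rate of 3.88% and a component reading of the coefficients, an inert feature would be credited 12% of the time when the other feature's effect is 0.095 points and about 24–25% at 0.19 points, against 5% for an adjacent-arm contrast. At 0.19 points, the allocations examined move the figure between 14% and 32%. Confirmatory Analysis 1, its alpha, the stopping rules and the sample size are unaffected. Pooling remains a defensible choice if an average over versions is what is wanted, provided it is labelled that way.

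**What to change.** In the three modified arms, fit one OLS model with both indicators (map = arms 3 and 4; self-triage = arm 4) and the planned distance covariates. Equivalently for this purpose, report arm 3 vs arm 2 and arm 4 vs arm 3, with intervals, from the Analysis 1 model. Do the same for urgent care visits, calls and portal messages. Keep the pooled contrasts only if they are described as averages over versions.

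State three limits:

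- The chart's effect can be estimated only in the presence of the map, because no arm has the chart alone.
- The map's effect includes the urgent care information that accompanies it.
- The change was made after the interim look but before the final outcome data were extracted (the position described in Project Status).

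The cost is one model line or two contrasts, with no new data. The SE is about 15% larger, and power for a 0.19-point map effect with an inert chart falls from about 60% to about 50%.
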